3.3 Documents used to create SAP

Documents used to create the SAP include:

- Early Adapter Part II Clinical Investigational Plan
- Early Adapter Part II Data Management Plan
- Early Adapter Part II eCRF Requirement

4. Study Objectives

4.1 Primary objective

To demonstrate decreased Total Electrical Energy Delivered (TEED) during adaptive (aDBS) as compared to continuous DBS (cDBS).

4.2 Secondary objective

To demonstrate maintenance within an optimal beta local field potential (LFP) threshold during aDBS mode compared to cDBS. The optimal beta LFP threshold indicates values between upper and lower LFP threshold of beta LFP power preset for each patient.

4.3 Safety assessment

To assess safety in the following items:

- Stimulation-related adverse events during the aDBS treatment phase
- Serious adverse events which occur through the study after consent and for which the relationship with Percept PC cannot be ruled out: for all subjects
- Any-cause of death throughout the study: for all subjects.
- Device (Percept PC) deficiencies that potentially involve a serious adverse event throughout the study: for all subjects

4.4 Additional objectives

To characterize clinical outcomes of aDBS (preferred mode) vs. cDBS, and by aDBS mode in the following items:

- EQ-5D-5L
- Parkinson's Disease Questionnaire (PDQ)-39
- Unified Dyskinesia Rating Scale (UDysRS)
- Movement Disorder Society-Sponsored Revision of Unified Parkinson's Disease Rating Scale (MDS-UPDRS) II ("best" and "worst" conditions)*
- MDS-UPDRS III and IV
- LFP dynamics based on out of clinic patient event markers and PD Medication cycle
- Movement data collected from Apple Watch (will be correlated with Percept Device data and clinical measures)
- To assess a patient-specific anatomy using a visualization tool of lead location and simulated volume of neural activation based on Pre-op/post-op imaging data of Percept PC implant.
- Patient preference of aDBS (preferred mode) vs cDBS
- Patient satisfaction with aDBS (preferred mode)
- Global Impression of Change (GIC) with aDBS
- Assess the average function of the subjects during the past week, including the assessment date, when they were in the "best conditions" and "worst conditions".

* "Best conditions" is the time period when PD subjects are receiving relief from their Parkinson's disease symptoms, also known as "on" time or "on" period. "Worst conditions" is the time period when PD subjects are not receiving relief from their Parkinson's disease symptoms, also known as "off" time or "off" period.

5. Investigation Plan

This is a prospective, randomized, single-blind, crossover, multicenter study of aDBS in subjects with Parkinson's disease. The study is expected to be conducted at two centers located in Japan. It is

estimated that approximately 20-30 subjects will be enrolled (implanted with a commercially available Medtronic DBS system with Percept PC INS) to obtain a study population of 20 subjects who complete the aDBS treatment phase. These subjects will roll over from the Early Adapter part I study or will qualify on the basis of demonstrated aDBS acceptability.

The expected study duration of the study is approximately 3 years. It is estimated an enrollment period of 14 months to enroll 20-30 subjects.

Study visits and/or phases include (see Figure 5-1 and Figure 5-2):

- Enrollment Visit: Consent
- Baseline: Demographics, Medical & surgical history, PD history, Device Information, MRI/ CT image data, Signal Test/LFP threshold setting, aDBS washout, Concomitant medications (non-PD), PD medication, Preference questionnaire and Device data programming session upload
- Randomization: 7 days or more after cDBS has been set and within 30 days after the baseline visit, subjects will be randomly assigned to aDBS mode (single or dual threshold) or cDBS.
- aDBS Treatment phase [Period A initiation (Visit A), Post Period A (Visit 2), Post Period B (Visit 3)]: Concomitant medications (non-PD), PD medications, Programming session upload, with device interrogation and BrainSense data included in the JSON session data report, PDQ-39, EQ-5D-5L MDS-UPDRS II ("best" conditions), MDS-UPDRS II ("worst" conditions), MDS-UPDRS III (On stim (cDBS)/On med) – trained rater, MDS-UPDRS IV – trained rater, UDysRS, Upload data collected from Apple Watch, including movement and sleep data
- Follow-up phase [Visit4, Visit5, Visit6]

Figure 5--1. Study Schematic

[figure not shown]

Figure 5--2. Study Procedures and Data Collection by Visit

Visit	Enrollment	Baseline	Randomization	aDBS Treatment Phase					Follow-up phase			Exit
				Visit 1	Out of clinic	Visit 2	Out of clinic	Visit 3	Visit 4	Visit 5	Visit 6	
Visit ranges (From the previous visit)		Up to 30 days		Up to 30 days		45 days ⁴		45 days ⁴	45-60 days ⁴	45-60 days ⁴	45-60 days ⁴	
Informed Consent	X											
Demographics		X ¹										
Medical & surgical history		X ¹										
PD history		X ¹										
Device Information		X ¹										
MRI/ CT image data		X ¹										
Signal Test/LFP threshold setting		X ¹										
aDBS washout (7 days or more)		X										

Early Adapter II Statistical Analysis Plan

Revision 1.0

Page 9 of 23

Form

Medtronic

Visit	Enrollment	Baseline	Randomization	aDBS Treatment Phase					Follow-up phase			Exit
				Visit 1	Out of clinic	Visit 2	Out of clinic	Visit 3	Visit 4	Visit 5	Visit 6	
Visit ranges (From the previous visit)		Up to 30 days		Up to 30 days		45 days ⁴		45 days ⁴	45-60 days ⁴	45-60 days ⁴	45-60 days ⁴	
Randomization			X									
Concomitant medications (non-PD)		X		X		X		X	X	X	X	
PD medication		X		X		X		X	X	X	X	
Program initiation (cDBS or aDBS)				X		X						
PDQ-39				X		X		X	X	X	X	
EQ-5D-5L				X		X		X	X	X	X	
UDysRS				X		X		X	X	X	X	
MDS-UPDRS II ("best" conditions)				X		X		X	X	X	X	
MDS-UPDRS II ("worst" conditions)				X		X		X	X	X	X	
MDS-UPDRS III				X		X		X	X	X	X	
MDS-UPDRS IV				X		X		X	X	X	X	
DBS GIC						X		X				
Preference questionnaire		X ¹						X ⁵				
Satisfaction questionnaire								X ⁵			X	
Apple Watch/iPhone distribution and programming				X								
Apple Watch/iPhone data collection				X	X ²	X	X ²	X	X	X	X	
Device data		X ³		X		X		X	X	X	X	
Event markers (Option)					X		X		X	X	X	
Adverse Events	As they occur											
Device Deficiencies	As they occur											
Protocol Deviations	As they occur											

Visit	Enrollment	Baseline	Randomization	aDBS Treatment Phase					Follow-up phase			Exit
				Visit 1	Out of clinic	Visit 2	Out of clinic	Visit 3	Visit 4	Visit 5	Visit 6	
Visit ranges (From the previous visit)		Up to 30 days		Up to 30 days		45 days ⁴		45 days ⁴	45- 60 days ⁴	45- 60 days ⁴	45- 60 days ⁴	
Reason for exit												X

¹ Not required if data collected prior to Early Adapter Part II

² PD Medication cycle, every 14 days during 45 days of Period A and B; Calendar reminders set on Apple Watch, with instructions

³ If Signal test was implemented

⁴ Visit ranges ± 7 days

⁵ Perform before unblinding subjects

⁶ Perform after unblinding subjects

6. Determination of Sample Size

Based on the registry data and the bench testing, when a conservative estimate for the first quartile of TEED data for initial devices in the registry is used, TEED is expected to decrease between 35 and 22 units for aDBS single threshold mode and aDBS dual threshold mode, respectively ^{1,2}. A standard deviation of 36 results in a medium to large effect size of 0.7858. Based on these assumptions, the sample size was estimated using a two-sided ($\alpha=0.05$) paired T-Test means (PASS 2019) to compare the difference in aDBS TEED to cDBS TEED of 28 and a standard deviation of 36, a minimum of 20 subjects achieves at least 90% power for the detection of an effect size of 0.78. It is anticipated that around 25% of subjects will have unilateral DBS and so they will be excluded from the primary analysis. Considering this information, it is estimated that between 20-30 subjects implanted with a commercially available Medtronic DBS system with Percept PC INS will be enrolled to obtain a study population of 20 (bilateral DBS).

7. Statistical Methods

7.1 Study Subjects

7.1.1 Disposition of Subjects

Subject disposition will be illustrated according to the extension of CONSORT Statement¹ for crossover trial and attrition will be identified and summarized. The number of subjects enrolled, randomized, and who underwent cDBS and aDBS adjustment phases will be summarized.

7.1.2 Clinical Investigation Plan (CIP) Deviations

CIP deviations will be listed and the number of deviations will be summarized by associated visit, type and overall.

7.1.3 Analysis Sets

The following subject sets will be used for the analysis:

- Complete Case (CC): includes all subjects with bilateral aDBS who initiate the aDBS treatment phase and have complete data for the respective analysis. This set will be used for the primary analysis.
- As-Treated (AT): includes all subjects who are treated with continuous Deep Brain Stimulation (cDBS) and/or adaptive Deep Brain Stimulation (aDBS) at enrollment and/or the aDBS treatment phase and uses the observed treatment used for each subject in each phase regardless unilateral or bilateral DBS. This set will be used for the safety assessment.
- Lead Complete Case (LCC): includes all subjects with aDBS who initiate the aDBS treatment phase and have complete data for the respective analysis regardless of unilateral or bilateral aDBS. This set will be used for the supporting analysis.

7.2 General Methodology

A formal analysis for the Early Adapter Part II study will occur when all active subjects have completed the aDBS treatment phase of the study. Analysis will include both the primary/secondary endpoints. Safety assessment and additional objectives will be addressed based on available data. A final report will be prepared once all data collection has ended and all subjects have completed the study or have been exited. The main analysis will include data from both contributing centers.

The subjects' baseline will be summarized with descriptive statistics. Summary statistics will be presented for continuous measures (N, means, medians, standard deviations, minimum and maximums) and categorical measures (N, percentage, frequency distributions) with 95% confidence intervals as appropriate. For events that can occur more than once in a single subject, such as adverse events, the percentage will be based on subjects experiencing the event; both subject and event counts will be reported. Summary statistics will be provided for each randomization group and period.

7.3 Center Pooling

All investigators will conduct the study according to a common protocol and utilize the same Case Report Forms (CRFs) to collect study data. Any efforts will be made to ensure consistency among sites in selection of patients and conduct of the study procedures. In addition, a poolability assessment based on the descriptive statistics of the primary and key secondary endpoints by center will be performed.

7.4 Handling of Missing, Unused, and Spurious Data and Dropouts

No imputation will be used. However, all attempts will be made to minimize missing data.

7.5 Adjustments for Multiple Comparisons

No adjustment will be performed for evaluations of the additional study objectives.

7.6 Demographic and Other Baseline Characteristics

Demographics and baseline characteristics will be summarized for the CC set. This will at least include:

- Baseline demographics: Age and Sex
- Medical and Surgery history: Disease name and Surgery name
- PD history: PD duration, Dyskinesia duration, Location of dyskinesias, Motor fluctuation duration, Dominant Side, Duration of L-DOPA treatment, Duration of dopamine agonist treatment
- Device identification information, including historical DBS implant information
- Signal test/LFP threshold setting
- aDBS washout (7 days or more)
- Patient preference questionnaire
- Concomitant medications (non-PD)
- PD medication
- Programming session upload, with device interrogation and BrainSense data included in the JSON session data report

The statistical evaluations will use some derived variables as listed below.

New Variable	Derivation
PD duration	Visit Year – PD diagnosis Year
Dyskinesia duration	Visit Year – Dyskinesia start Year
Motor fluctuation duration	Visit Year – Motor fluctuation start Year
Duration of L-DOPA treatment	Visit Year – L-DOPA treatment start Year
Duration of dopamine agonist treatment	Visit Year – L-DOPA treatment start Year
Study Exposure (days)	(Study Exit date – Consent date)/30.44

7.7 Treatment Characteristics

Device data will be summarized with descriptive statistics as described in section 7.2.

In addition, duration of study exposure will be measured in days starting from the point of enrollment (informed consent completed) through and including the time of study exit: duration of study exposure (days) = (study exit date – date of consent). Extent of study exposure will be presented in a summary table and supporting data listing if needed.

7.8 Interim Analyses

No interim analysis is planned for this study.

7.9 Evaluation of Objectives

7.9.1 Primary Objective

The primary objective is to demonstrate decreased Total Electrical Energy Delivered (TEED) during adaptive (aDBS) as compared to continuous DBS (cDBS).

7.9.1.1 Endpoint definition

The endpoint is the energy use as measured by TEED during the aDBS as compared with TEED during the cDBS during the aDBS treatment phase (from period A to period B). Denote by $TEED_{aDBS}$ the TEED on aDBS and by $TEED_{cDBS}$ the corresponding value for cDBS. For each patient the difference between $TEED_{aDBS}$ and $TEED_{cDBS}$ will be calculated ($TEED_{aDBS} - TEED_{cDBS} = TEED_{DIFF}$).

7.9.1.2 Hypothesis

The hypothesis that $TEED_{DIFF} < 0$ will be tested by means of the Student's paired t-test and a p-value less than, or equal to, 0.05 will be regarded statistically significant. As a robustness analysis the hypothesis will be tested by means of the Wilcoxon signed rank test as well.

The formal hypothesis testing is:

$$H_0: \mu TEED_{aDBS} - \mu TEED_{cDBS} = 0 \quad \text{vs.} \quad H_a: \mu TEED_{aDBS} - \mu TEED_{cDBS} < 0,$$

where the difference $\mu TEED_{DIFF} = \mu TEED_{aDBS} - \mu TEED_{cDBS}$ is the mean electrical energy saving.

TEED is defined as the total energy delivered by an electrical system through the DBS leads over an arbitrary period of time.

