Sample Size	
The sample size was estimated using a one-sided test ($\alpha=0.025$) for paired T-Test means (PASS 2019) to compare the difference in aDBS TEED to cDBS TEED of 22 and a standard deviation of 28, a minimum of 20 subjects achieves at least 90% power for the detection of an effect size of 0.79. These subjects will roll over from the Early Adapter 1 study or will qualify on the basis of demonstrated aDBS acceptability.

Inclusion/Exclusion Criteria	
Inclusion Criteria
 
 1. Subject has Parkinson's disease with motor impairments. 2. Subject is implanted with Percept PC and Medtronic DBS leads and extensions bilaterally in the same target (physician confirmed), STN or GPi. 3. Subject has completed Early Adapter 1 study OR if the subject has not completed Early Adapter 1, she/he has documented evidence that aDBS is well tolerated in at least one mode (single or dual threshold) (Note: Tolerance means that the investigator has determined that aDBS is suitable for PD treatment). For subject who only tolerated dual threshold mode, aDBS must be set up in both hemispheres.* 4. Subject has Beta band (8-30 Hz) amplitude $\geq 1.2 \mu Vp$ detected on either left and/or right DBS leads on sensing channels 0-2, 0-3, or 1-3; 8-10, 8-11, or 9-11; As assessed in screening from Early Adapter I study. For subjects who have not completed Early Adapter Part I, it can be assessed using the record of standard test of eligibility for aDBS at the site. 5. The subject responds to DBS Therapy. 6. The subject's cDBS parameters and PD medications are stable and expected to remain stable from enrollment through the end of the aDBS treatment phase. (Note: Stability is defined as no major changes in cDBS parameter and medication for the last 30 days prior to aDBS setup or as defined by the physician.)

7. Subject is configured to monopolar or dual monopolar stimulation using contacts 1 and/or 2 (9 and/or 10) on at least one side
8. Subject is willing and able to attend all study-required visits and complete the study procedures.
9. Subject has the ability to understand and provide written informed consent for participation in the study prior to the study-related procedures being conducted.
10. Subject is a male or non-pregnant female. If female of childbearing potential, and if sexually active, must be using, or agree to use, a medically acceptable method of birth control as confirmed by the investigator.

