12.1 General Aspects of Analysis

Data analysis will be performed by Medtronic-employed statisticians or designees. All statistical analyses will be performed using Statistical Analysis System (SAS) for Windows (version 9.4 or higher, SAS Institute Inc. Cary, NC), R (version 3.2 or higher, R Foundation for Statistical Computing, Vienna, Austria) or any validated statistical software.

In the primary analysis report, continuous data will be summarized using standard descriptive statistics including the mean, standard deviation, median and range or interquartile range. Categorical variables will be summarized using frequency counts and percentages. For events that can occur more than once in a single subject, such as adverse events, the percentage will be based on subjects experiencing the event; both subject and event counts will be reported. P-values will be two-sided, with values less than 0.05 indicating statistical significance.

Since the impact of missing data is expected to be small no multiple imputation method for missing data is planned.

The Gatekeeping procedures will be applied for the multiple testing procedures. After the primary study objective is met ($\alpha=0.05$, two-sided gatekeeper), the secondary study objective will be carried out at $\alpha=0.05$ two-sided. No multiplicity adjustment will be performed for evaluations of the additional study objectives. No imputation will be used.

The analyses will use two population sets:

- The Complete Case set (CC) analysis includes all patients enrolled in the study those sign Patient Informed Consent, fulfill the inclusion and exclusion criteria and randomized who initiate the aDBS treatment phase and have complete data for the respective analysis. The CC set will be used for primary and secondary objectives.
- The As-Treated Set (AT) includes subjects who are treated with continuous Deep Brain Stimulation (cDBS) and/or adaptive Deep Brain Stimulation (aDBS) at enrollment and/or the aDBS treatment phase and uses the observed treatment used for each subject in each phase. This set will be used for safety assessment.

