12.4 Primary Objective

The primary objective is to demonstrate decreased Total Electrical Energy Delivered (TEED) during adaptive (aDBS) as compared to continuous DBS (cDBS). For this endpoint the CC cohort will be used.

The endpoint is the energy use as measured by TEED during the aDBS as compared with TEED during the cDBS during the aDBS treatment phase (from period A to period B). Denote the TEED on aDBS by $TEED_{aDBS}$ and the corresponding value for cDBS by $TEED_{cDBS}$. For each patient the difference between $TEED_{aDBS}$ and $TEED_{cDBS}$ will be calculated ($TEED_{aDBS} - TEED_{cDBS} = TEED_{DIFF}$). The hypothesis that $TEED_{DIFF} \neq 0$

will be tested by means of the Student's paired t-test and a p-value less than, or equal to, 0.025 will be regarded statistically significant. The formal hypothesis testing is:

$$H_0: \mu_{\text{TEEDaDBS}} - \mu_{\text{TEEDcDBS}} = 0$$

$$H_a: \mu_{\text{TEEDaDBS}} - \mu_{\text{TEEDcDBS}} \neq 0$$

Where the difference ($\mu_{\text{TEEDaDBS}} - \mu_{\text{TEEDcDBS}}$) is the electrical energy saving.

TEED is defined as the total energy delivered by an electrical system through the DBS leads over an arbitrary period of time. TEED is determined by the stimulation parameters (e.g., pulse width, frequency, amplitude) and the measured impedance.

The calculation of TEED when using constant voltage is:

$$\text{TEED} = (\text{Voltage}^2 * \text{Frequency} * \text{Pulse width}) / \text{Impedance}$$

The calculation of TEED when using constant current is:

$$\text{TEED} = \text{Current}^2 * \text{Frequency} * \text{Pulse width} * \text{Impedance}$$

The previous formulas can be used without modification with legacy lead.

When the lead is a directional lead with separate electrodes and it is programmed in Directional Stim Mode or Ring Mode Stimulation, each contact is considered independent. For each segment that is activated, TEED will be calculated individually using the formulas above, and then summed to obtain the total TEED for the lead. Leads programmed with monopolar settings will use the electrode unipolar impedance between the case and the active electrode. If 2 cathodes are used (dual monopolar settings), TEED will be calculated for each contact separately, and total TEED will be determined for the lead as the sum of the two TEED. Leads programmed to bipolar will use the impedance between the active electrodes.

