12.5 Secondary Objective

The following secondary objective has specific hypothesis to be tested. This key secondary objective will be tested under a Gatekeeping strategy for the multiple testing procedures. After the primary study objective is met (gatekeeper), this secondary study objective will be carried out at $\alpha=0.05$ and a p-value less than 0.05 two-sided will be considered met as long as the primary objectives above it have also been met.

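### The primary test has three different success rules (two-sided p ≤ 0.025, two-sided p < 0.05, one-sided p ≤ 0.05), so the same data can pass or fail, and the SAP rule doubles the planned false-positive rate.

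*SAP*

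**What the plan says.** The rule for the primary TEED comparison appears in several places in the current text.

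- **SAP 7.9.1.2.** The alternative, in words and in symbols, is that the aDBS minus cDBS difference is below zero. The criterion is "a p-value less than, or equal to, 0.05 will be regarded statistically significant".
- **Protocol 12.4.** The alternative is that the difference is not equal to zero. The criterion is "a p-value less than, or equal to, 0.025 will be regarded statistically significant".
- **Protocol 12.1.** "P-values will be two-sided, with values less than 0.05 indicating statistical significance". The same section and the synopsis (Statistics) make the primary objective the gatekeeper at two-sided 0.05.
- **Sample size.** The synopsis states: "The sample size was estimated using a one-sided test", with alpha 0.025. Protocol 12.8 and SAP section 6 state a two-sided test with alpha 0.05. For a TEED decrease these are the same test.

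On the secondary endpoint, Protocol 12.5 says: "After the primary study objective is met (gatekeeper), this secondary study objective will be carried out at" alpha 0.05, two-sided. SAP 7.5, the section on multiple comparisons, contains only this: "No adjustment will be performed for evaluations of the additional study objectives". SAP 7.9.2 gives neither a gate nor a significance level for the secondary test.

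**The concern.** The opening of Protocol section 12 makes the study successful when the primary objective is met, so the threshold and sidedness of this one test decide the headline result. Three rules are in force at once and no text ranks them. Protocol 12.2 requires departures from the planned methods to be documented in the SAP with a statistical rationale. SAP 7.9.1.2 changes both sidedness and threshold relative to Protocol 12.4 and gives none. It also departs from SAP section 6, which SAP 7.9.1.3 cites as the sample-size justification for this same test.

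Three things are at stake: the error rate attached to a claim of lower TEED, whether 20 completers give the stated power, and whether the secondary test is opened. If the conflict is still there at analysis, the choice among rules can be made with the result in view.

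**Working it through.** **Inputs.** n = 20 and power of at least 90% (Protocol 12.8, SAP 6). Difference 22 and SD 28 (Protocol 12.8 and synopsis), or difference 28 and SD 36 (SAP 6).

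**Formulas.** For a paired t-test with df = n − 1 = 19:
- noncentrality = (difference / SD) × √n, which is (22/28) × √20 = 3.51 or (28/36) × √20 = 3.48;
- power = probability that a noncentral t with this noncentrality exceeds the critical t;
- smallest significant mean saving = critical t × SD / √n, where 28/√20 = 6.261 and 36/√20 = 8.050;
- false-positive rate for a claimed decrease = alpha for a one-sided test, alpha/2 for a two-sided test.

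**Reproducing the plan.** At two-sided 0.05 (equivalently one-sided 0.025), n = 20 gives 91.5% power with 22/28 and 91.0% with 28/36. The smallest n reaching 90% is 20 in both cases. The stated sample size is therefore right for that rule.

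**The three rules at n = 20:**

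| | SAP 7.9.1.2, one-sided 0.05 | Protocol 12.1 and synopsis, two-sided 0.05 | Protocol 12.4, two-sided 0.025 |
|---|---|---|---|
| Critical t | 1.729 | 2.093 | 2.433 |
| Saving needed, SD 28 | 10.83 | 13.10 | 15.24 |
| Saving needed, SD 36 | 13.92 | 16.85 | 19.59 |
| Power, 22/28 | 95.9% | 91.5% | 85.0% |
| Power, 28/36 | 95.6% | 91.0% | 84.2% |
| n for 90%, 22/28 | 16 | 20 | 23 |
| n for 90%, 28/36 | 16 | 20 | 24 |
| False claim of a decrease | 5% | 2.5% | 1.25% |

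**Examples.** An observed t of −1.9 (one-sided p = 0.036, two-sided p = 0.073) passes only the SAP rule. An observed t of −2.2 (one-sided p = 0.020, two-sided p = 0.040) passes the SAP and Protocol 12.1 rules and fails Protocol 12.4.

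**How often the rules disagree.** At the planned effect (22/28), the chance of passing the most lenient rule but not the strictest is 95.9% − 85.0% = 10.9%. Between the SAP rule and two-sided 0.05 it is 95.9% − 91.5% = 4.4%. If the true standardised effect were 0.5 rather than 0.786, the pass rates would be 69.5%, 56.5% and 43.9%, and the first gap would be 25.6%.

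**The case against.** The strongest reply is that the documents have one dominant design basis, two-sided 0.05, and two badly worded hypothesis paragraphs. SAP 7.9.1.2 never uses the term one-sided. Read with SAP section 6 and Protocol 12.1, its p-value could be two-sided, and then nothing doubles. Likewise, the 0.025 in Protocol 12.4 could be the synopsis's one-sided threshold left beside a two-sided hypothesis, and then power is 91.5%, not 85.0%. These are plausible accounts of how the texts arose. But each needs words that the paragraph does not contain: a directional hypothesis judged at 0.05 is on its face a one-sided 5% test, and a not-equal alternative judged at 0.025 is on its face a two-sided 2.5% test. Writing the benign reading down is exactly the correction asked for.

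Three smaller points stand:

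- The cut-offs in TEED units hold only for n = 20, an observed SD equal to the planning value, and the t-test. A Shapiro-Wilk p below 0.05 moves the primary analysis to the Wilcoxon signed-rank test, where the same conflict over alpha applies but the unit cut-offs do not.
- Nominal alpha summed over both tails is 5% for one-sided 0.05 and two-sided 0.05 alike. What doubles is the error in the direction of benefit.
- SAP silence on gatekeeping does not contradict the protocol. It is an omission, and the main point does not rest on it.

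**Conclusion.** The concern holds. The current texts give three success rules for the test that defines study success, and none is said to govern. Taken as written, the SAP rule allows a 5% chance of falsely claiming lower TEED, twice the planned 2.5% and four times the 1.25% of Protocol 12.4. The Protocol 12.4 rule gives 85.0% power (84.2% with the SAP's planning values) instead of at least 90%, and would need 23 (or 24) completers. With n = 20 and SD 28, a mean saving between 10.8 and 15.2 units succeeds under one text and fails under another; with SD 36 the range is 13.9 to 19.6 units. These figures assume the paired t-test, and that each hypothesis paragraph is read by its own stated alternative. The sample size of 20 is not in error. It matches two-sided 0.05. Because the conflict can reverse the headline conclusion, it must be resolved before the data freeze for the primary analysis.

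**What to change.** Adopt one rule everywhere: a two-sided paired comparison at alpha 0.05 (equal to one-sided 0.025 for a decrease), with the primary objective met only if p < 0.05 and the aDBS minus cDBS difference is negative.

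- **Protocol 12.4:** replace the 0.025 threshold and add the condition on direction.
- **SAP 7.9.1.2:** replace the directional test at 0.05 with the same rule, and state that it also applies if the Wilcoxon signed-rank test is used.
- **Protocol synopsis (Sample Size):** either state the two-sided form or note that one-sided 0.025 is equivalent.
- **SAP 7.5:** state that the secondary endpoint is tested at two-sided 0.05 only if the primary objective is met.

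No subjects or data are added, since this is the rule the 20 completers were sized for. The cost is procedural. Under Protocol 14.7 the protocol wording needs an amendment approved by the ethics committee before it is implemented. Under SAP 7.11 a change to a principal feature, which the primary success rule is, needs a SAP amendment.
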